9.3.6. Participant Diary Card

Participants will be given a diary card for them to record the healing time of the blisters as well as to record any adverse events or medications taken whilst outside of the unit.

9.3.7. Pain scale

After the final blister sample in each session is taken, participants will be asked to rate their level of pain from blister induction on an 11-point scale (0-10), with 0 being "no pain" and 10 being "worst pain imaginable" (Farrar, 2001).

9.3.8. Clinical Safety Laboratory Assessments

- Refer to Appendix 2 for the list of clinical laboratory tests to be performed and to the SoA for the timing and frequency.
- The investigator must review the laboratory report, document this review, and record any clinically relevant changes occurring during the study in the AE section of the CRF. The laboratory reports must be filed with the source documents. Clinically significant abnormal laboratory findings are those which are not associated with the underlying disease, unless judged by the investigator to be more severe than expected for the participant's condition.
- All laboratory tests with values considered clinically significantly abnormal during participation in the study or within 7 days after the last dose of study treatment should be repeated until the values return to normal or baseline or are no longer considered significantly abnormal by the investigator or medical monitor.
- If such values do not return to normal/baseline within a period of time judged reasonable by the investigator, the aetiology should be identified and the sponsor notified.
- All protocol-required laboratory assessments, as defined in Appendix 2, must be conducted in accordance with the laboratory manual and the SoA.

9.4. Genetics

Genetics are not evaluated in this study. Transcriptome analysis will utilise Next Generation Sequencing (NGS) methods, which are described in Section 9.7.1.4.

9.5. Pharmacokinetics

Pharmacokinetics are not evaluated in this study.

9.6. Pharmacodynamics

Some of the pharmacodynamic endpoints may be reported separately from the main clinical study report.

9.7. Biomarkers

There will be several different types of biomarker samples collected during the study, as outlined in the SOA, including biomarkers from blood, urine and blister fluid. Some of the exploratory biomarkers may be reported separately from the main clinical study report.

9.7.1. Biomarkers in blood

9.7.1.1. Mediators blood sample

Approximately 6 mL of blood will be collected into SST or Na Heparin tubes according to the timings on the SoA. This will allow for analysis of serum (or plasma) to measure inflammatory mediators. Methods of analysis which may be used on these samples are detailed in the Study Reference Manual. Measurement of soluble inflammatory mediators will be carried out in batch analysis.

9.7.1.2. Flow cytometry blood sample

Blood samples of approximately 2 mL will be collected into SST or Na Heparin tubes for measurement of leukocyte number and activation markers by flow cytometry (see indicative list in endpoints), at times specified in the SoA.

9.7.1.3. *Ex vivo* stimulation blood sample

For the LPS challenge participants only, 2x 1 mL whole blood samples will be collected at pre-dose and 6 hours post-LPS dose. These samples will be drawn into TruCulture tubes containing LPS and the other in a TruCulture null tube, and incubated for 24 hours. Cellular and soluble contents will be separated and inflammatory mediators analysed in the soluble fraction.

9.7.1.4. Transcriptome blood sample

In session 2, whole blood will be collected into PAXgene tubes for transcriptome analysis. Blood (2.5 ml) will be collected prior and several time points post LPS or GM-CSF challenge as detailed in SoA. Samples will be used to extract RNA and prepare cDNA which will subsequently be used for transcriptome analysis by Next Generation Sequencing (NGS) methods. NGS data will be aligned and mapped to human genome reference sequences and analysed for differential expression for each challenge type.

9.7.2. Biomarkers in urine

The pre-challenge urine sample will be collected during session 1. The post-challenge urine samples will be collected during session 2 after LPS challenge. In session 2, participants will be encouraged to pass urine immediately before LPS challenge dose and urine voids will be collected from after LPS until 12 hours post-LPS and the time of the urine collection will be recorded. These samples will be collected for measurement of tetranor-PGDM and other inflammatory mediators. Tetranor-PGDM is the stable urinary metabolite of the prostaglandin PGD2. While tetranor-PGDM has very low natural abundance in normal healthy individuals, it has been shown to be elevated in the urine of patients with Duchenne muscular dystrophy. Elevation of urinary tetranor-PGDM in normal healthy volunteers through LPS challenge would allow for evaluation of target engagement in that population Tetranor-PGDM and related metabolite will be measure by mass spectroscopy as samples are collected.

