5. STUDY DESIGN

5.1. Overall Design

This is an exploratory study comprising of 2 parts. In both parts of the study, participants will have 2 sessions. In session 1 (baseline) all participants will have 2 blisters induced on each forearm by application of cantharidin solution (based on method described by Day et al. (Day, 2001)) followed by blood draws and a blister harvest on each forearm at 24 and 48 hours post-induction. After a minimum of 14 days blister healing period, participants will return for a second session (*in vivo* challenge session). This open label study will randomise participants to have either a LPS or GM-CSF *in vivo* challenge (4 completed participants in each group). Participants will then have 2 blisters induced on each forearm by application of cantharidin solution, followed by multiple, timed, blood draws (15 minutes to 48 hours post dose) and a blister harvest on each forearm at 24 and 48 hours post-induction.

In part I of the study, a dose exploration of each of the challenge agents (LPS and GM-CSF) will be required to find a dose that provides a robust inflammatory response. Up to 6 cohorts of 4 participants will be tested and all cohorts will have 2 sessions, as described above. For Part I, an initial cohort of 4 participants (Cohort 1) will proceed with session 1. After their blister healing period, Cohort 1 will return for their session 2 visit in two groups of 2 participants (Group A and Group B) on different days. Group A will be dosed on the same day (one with LPS and one with GM-CSF) and Group B will be dosed on a different day (one participant with LPS and one participant with GM-CSF) after group A. Once all 4 participants have been dosed, a dose escalation meeting will be held to make an assessment of tolerability and inflammatory response from the first Cohort (e.g. the primary endpoints) to determine the dose for Cohort 2. This dose escalation meeting will be held prior to Group A in Cohort 2 proceeding to be dosed with the challenge agents in Session 2. This same dose escalation procedure will continue until a well-tolerated dose for LPS and GM-CSF showing a robust inflammatory response has been identified. Once the well-tolerated dose with robust inflammatory response has been determined, additional participants will be administered this same dose until there are 8 evaluable participants (4 with LPS at the same dose and 4 with GM-CSF at the same dose) completed in Part I.

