9. STUDY ASSESSMENTS AND PROCEDURES

- Study procedures and their timing are summarized in the SoA (Section 2).
- Protocol waivers or exemptions are not allowed
- Immediate safety concerns should be discussed with the sponsor immediately upon occurrence or awareness to determine if the participant should continue or discontinue study treatment.
- Samples will be stored securely and made accessible only to scientists contributing to and supporting this research. Clear custodianship responsibilities will be in place at all times and receipt/use/disposal details will be tracked on databases as per GSK internal processes. The samples will be stored for a maximum of 5 years, after which they will be disposed of in accordance with the Human Tissue Authority's Code of Practice.
- Adherence to the study design requirements, including those specified in the SoA, is essential and required for study conduct.
- All screening evaluations must be completed and reviewed to confirm that potential participants meet all eligibility criteria. The investigator will maintain a screening log to record details of all participants screened and to confirm eligibility or record reasons for screening failure, as applicable.

- The maximum amount of blood collected from each participant over the duration of the study, including any extra assessments that may be required, will not exceed 500 mL.
- Repeat or unscheduled samples may be taken for safety reasons or for technical issues with the samples.

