Dose Escalation Criteria	
Below is the Dose Escalation Criteria decided by the study team                      If only one participant hits stopping criteria then there will be a presumption of stopping escalation, unless in the judgement of the team further escalation would provide additional scientific value to the study without materially impacting on participant wellbeing.
 
LPS: STOP dose escalation, IF:
 
 
• Peak plasma/serum level of TNF-<math>\alpha</math> <math>\geq</math> 100 pg/mL (minimum increase of 75 pg/ml from baseline) AND
 
• Peak plasma/serum level of IL-6 <math>\geq</math> 200 pg/mL (minimum increase of 100 pg/ml from baseline) AND
 
• Urinary tetranor PGDM 3x over baseline in urine OR
 
• Presence of adverse clinical signs (fever, HR + others) which, in the opinion of the investigator, pose an unacceptable risk to participants were dose escalation to proceed. Examples may include, but are not limited to:                             
 
○ Rigors
 
○ Meningeal symptoms of moderate severity
 
○ Vomiting
 
○ Clinically significant hypotension, hypertension, tachycardia or bradycardia
 
 
 
 
GM-CSF: STOP dose escalation IF:
 
 
• Max change of circulating total leukocyte counts increase by 5 giga/L OR
 
• Presence of adverse clinical signs (fever, HR + others) which, in the opinion of the investigator, pose an unacceptable risk to participants were dose escalation to proceed. Examples may include, but are not limited to:                             
 
○ Rigors
 
○ Meningeal symptoms of moderate severity
 
○ Vomiting
 
○ Clinically significant hypotension, hypertension, tachycardia or bradycardia
 
 
 
• Elevation of platelet count above 500 x 10^9/L
 

Dose Escalation Decision	
 
• Following each dose escalation meeting, the decision to STOP or dose escalate for each challenge agent was documented,
 
• An optimum dose of 0.75 ng/kg for LPS and 60 ug/m^2 for GM-CSF was identified.
 

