### 3.2. Interim Analyses

Interim Analysis	Details
Study Review Committee	Core GSK members include: 
 
• Study Physician Lead or their delegate; SERM; Statistician; Operations Study Lead; Epigenetics DPU, MM DPU, Scientific Operations Director, Clinical Development Manager.
 

Timing	
 
• At the end of Part I, an interim analysis will be conducted to decide whether to enrol additional participants in Part II of the study, for the optimum dose of 0.75 ng/kg for LPS and 60 ug / m2 for GM-CSF selected in Part I.
 

Biomarker Data Required	
 
• Data for Biomarkers listed in Section 10.3.3 will be presented in tabular and graphical format and summarized descriptively according to GSK's IDSL standards.
 

Statistical Analyses	
 
• There are no planned formal statistical analyses of the data. Descriptive summaries and/or graphical presentations will be presented, including data listings.
 

Criteria for Part II	
If at least one participant meets the criteria below for the optimal dose of 0.75ng/kg for LPS challenge or 60 ug/m2 for GM-CSF challenge, then Part II of the study will be initiated.
 
Participants will be enrolled to Part II – LPS Challenge at the dose level 0.75 ng/kg if for at least one participant:
 
 
• Maximum increase from baseline at any timepoint in plasma level of TNF-<math>\alpha</math> < 50 pg/mL AND
 
• Maximum increase from baseline at any timepoint in plasma level of IL-6 < 50 pg/mL AND
 
• Maximum increase from baseline at any timepoint in urinary tetranor PGDM level < 1.3x
 
 
Participants will be enrolled to Part II – GM-CSF Challenge at the dose level 60 ug/m2 if for at least one participant:
 
 
• Maximum increase from baseline at any timepoint in total leukocyte counts < 5 giga/L
 
• Note: Available data from all biomarkers will be considered before making the decision to move to Part II – GM-CSF Challenge.
 

Part II Decision	
 
• The decision to STOP after Part I or CONTINUE to Part II for each challenge agent will be documented, including any supporting data.
 

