#### 7.1.2. Summary Measure

Challenge	Endpoint
LPS	Absolute values and change from baseline in TNF- $\alpha$ , IL-6 and PGDM across the time course Baseline: 
 
• TNF-<math>\alpha</math>, IL-6: Session 2: Day 1 (Pre Blister Induction)
 
• PGDM: Session 1 Day 2 (Pre Fluid Sampling)
 

GM-CSF	Absolute values and change from baseline in total leukocyte across the time course 
 
• Baseline = Session 2: Day 1 (Pre Blister Induction)
 

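### The plan does not require a participant's baseline and post-LPS urine to share an assay run, so between-run shift can enter the tetranor-PGDM fold-change, an LPS primary endpoint

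*Protocol*

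**What the plan says.** Protocol 9.7.2 (Biomarkers in urine) sets the assay timing: "Tetranor-PGDM and related metabolite will be measure by mass spectroscopy as samples are collected". The same section places the two halves of the comparison in different sessions. For the baseline, "The pre-challenge urine sample will be collected during session 1". For the response, "urine voids will be collected from after LPS until 12 hours post-LPS", in Session 2. SAP 7.1.2 fixes the baseline as "PGDM: Session 1 Day 2 (Pre Fluid Sampling". Protocol 5.1 sets the gap: "After a minimum of 14 days blister healing period, participants will return for a second session".

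The ratio to baseline is then used twice in the SAP:
- Escalation (SAP 3.1): one component of the LPS biomarker stop is "Urinary tetranor PGDM 3x over baseline in urine".
- Part II (SAP 3.2): one component of the LPS trigger is "Maximum increase from baseline at any timepoint in urinary tetranor PGDM level" being under 1.3x.

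In both places PGDM is joined by AND to conditions on TNF-alpha and IL-6.

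Other assays are treated differently. Protocol 9.7.1.1 sends blood mediators to batch analysis. Protocol 5.1 defers and batches secondary and exploratory samples that do not need immediate assay. Neither provision covers urinary PGDM. The documents do not state how urine is allocated to runs, and they give no bridging control or between-run precision for this assay. The codes listed in SAP 10.3.3 include no run identifier.

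**The concern.** A fold-change is protected from calibration drift when numerator and denominator are measured in the same run, because the run's shift cancels. If the Session 1 sample is measured soon after Session 1 and the voids soon after Session 2, that protection is lost. The shift becomes a multiplicative error in the participant's ratio. Collecting more voids does not remove it: voids measured together share one shift, and every void is divided by the same baseline.

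Three things are exposed: a primary endpoint, the PGDM component of two rules applied participant by participant, and the in-house PGDM estimates. Protocol 10.1 says existing PGDM estimates are very limited and that Part I is meant to supply them.

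**Working it through.** **Plan's own figure.** There is none to reproduce. Protocol 10.1 gives no variability for PGDM, and its probability-of-success figures concern cytokines.

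**Inputs from the documents.** Baseline in Session 1 Day 2 (SAP 7.1.2); voids in Session 2 (Protocol 9.7.2); at least 14 days between sessions (Protocol 5.1); cut-offs of 3x (SAP 3.1) and 1.3x (SAP 3.2), both read here as ratios to baseline.

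**Assumed inputs.** Between-run CV of 5%, 10%, 15% or 20%; independent, log-normal run shifts; all of a participant's Session 2 voids in one run; no other error.

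**Model.** Observed ratio = true ratio x exp(e2 - e1), where e1 and e2 are the log shifts of the Session 1 and Session 2 runs, each with variance ln(1 + CV^2). If both samples share a run, e1 = e2 and the multiplier is exactly 1 at any CV. For separate runs:
- SD of the log multiplier: s = sqrt(2 x ln(1 + CV^2))
- 95% range of the multiplier: exp(-1.96 s) to exp(+1.96 s)
- Chance that a true ratio T reads below a cut-off c: Phi(ln(c/T)/s)

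Example at CV 10%: ln(1.01) = 0.00995, so s = sqrt(0.0199) = 0.141. The range is exp(-0.2765) to exp(+0.2765), or 0.76 to 1.32. For T = 1.5 and c = 1.3, ln(1.3/1.5) = -0.1431 and -0.1431/0.141 = -1.01, giving Phi = 15.5%.

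| Assumed CV | s | 95% multiplier | True 1.5x reads <1.3x | True 3.5x reads <3x | No response reads >=1.3x |
|---|---|---|---|---|---|
| 5% | 0.071 | 0.87-1.15 | 2.1% | 1.5% | 0.01% |
| 10% | 0.141 | 0.76-1.32 | 15.5% | 13.7% | 3.1% |
| 15% | 0.211 | 0.66-1.51 | 24.9% | 23.2% | 10.7% |
| 20% | 0.280 | 0.58-1.73 | 30.5% | 29.1% | 17.4% |

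A participant with no response would almost never read 3x: the chance is below 0.01% even at 20%. The 1.3x cut-off is the sensitive one.

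**Effect on the variability estimate (illustration only).** No PGDM SD is given, so borrow the log-scale SD of 0.217 that Protocol 10.1 assumes for TNF-alpha; its variance is 0.0471. With independent shifts per participant, separate runs add s^2 = 0.0199 at CV 10%, an increase of 0.0199/0.0471 = 42%. At CV 15% they add 0.0445, an increase of 94.5%. If participants share runs, part of the shift moves the mean instead of widening the SD.

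**From marker to rule.** The biomarker stop in SAP 3.1 also needs peak TNF-alpha of at least 100 pg/mL and peak IL-6 of at least 200 pg/mL, each with a minimum rise. The LPS trigger in SAP 3.2 also needs rises below 50 pg/mL in both cytokines in the same participant. A PGDM shift can therefore block either rule, but can complete one only where both cytokines already qualify.

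**The case against.** The strongest reply is that separate runs are inferred, not stated. No section allocates urine to runs. The sentence in Protocol 9.7.2 may mean only rolling analysis, in contrast to one end-of-study batch. PGDM is first needed at a review held after Session 2 dosing (Protocol 5.1, SAP 3.1), so running both sessions' urine together at that point is compatible with the text. This stands. It is why the point is that the plan fails to require a shared run, with the literal wording pointing the other way.

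A second reply is that the phrase is read literally between sessions but loosely within Session 2, where the voids are assumed to share a run. This partly stands. If voids were split across runs, e2 would vary from void to void. The baseline shift e1 would still be common to all of them, and the Part II rule takes the maximum, which favours upward shifts, so the error would change form but not disappear.

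Third, the size rests wholly on assumed CVs. At 5% the effect is small, so the documents alone cannot show that it is material. This stands.

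Fourth, the study is exploratory, with no formal hypotheses and a descriptive interim analysis, and adverse clinical signs can stop escalation independently of the biomarkers. This stands and limits the weight of the point.

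Fifth, frozen storage may not be safe for this analyte. Protocol 9.7.2 calls the metabolite stable, and Protocol 9 says "The samples will be stored for a maximum of 5 years". The first describes the metabolite and the second is a retention limit; neither is freezer-stability data. This stands, and the fix allows for it.

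**Conclusion.** The point holds as a gap with a cheap remedy. The plan states a rolling assay for urinary PGDM, specifies batching elsewhere, and does not require the two halves of a primary-endpoint ratio to share a run. If they do not, the spurious multiplier has a 95% range from 0.87-1.15 (assumed CV 5%) to 0.58-1.73 (assumed CV 20%). These figures depend on the assumed CVs and on independent run shifts.

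A reader might infer three stronger things, and the documents support none of them:
- That the samples were in fact assayed in separate runs. The run allocation is not given.
- That up to about 30% of decisions would be wrong. That figure is a single-marker misreading rate, and PGDM never acts without TNF-alpha and IL-6 in either biomarker rule.
- That the selected LPS dose was misidentified. SAP 3.1 reports escalation as complete, and nothing there shows that a PGDM shift affected it.

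The exposure that remains is the LPS Part II rule and the PGDM response and variability estimates.

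**What to change.** Replace the assay-timing sentence in Protocol 9.7.2 with a requirement along these lines: the Session 1 urine aliquot is stored and assayed in the same LC-MS run as that participant's Session 2 voids, after Session 2 and before the review that uses the result, and the run identifier is recorded with each value. If frozen-storage stability of tetranor-PGDM is not established, require instead common bridging QC samples in every run, and report the between-run precision they show. If both sessions are already run together in practice, the new sentence simply makes that binding.

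The cost is short frozen storage and one more recorded field. The baseline value would not be known before Session 2, but no rule uses it then. Results would still reach each review on time, because they are needed only after Session 2 dosing.

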9.7.3. Biomarkers in blisters

Biomarkers in blisters will be sampled at 24 and 48 hours post blister induction and collected in polypropylene micro-centrifuge tubes. Cellular and soluble contents will be separated. The volume of the blister sample will be calculated and recorded in the eCRF.

9.7.3.1. Flow cytometry blister sample

Blister sample will be used to measure leukocyte number and activation markers by flow cytometry (see indicative list in endpoints), at times specified in the SoA.

9.7.3.2. Mediators blister sample

The soluble fraction from the blister sample will be used to measure inflammatory mediators. Methods of analysis which may be used on these samples are detailed in the Study Reference Manual.

9.8. Health Economics OR Medical Resource Utilization and Health Economics

Health Economics/Medical Resource Utilization and Health Economics parameters are not evaluated in this study.

10. STATISTICAL CONSIDERATIONS

This is an exploratory enabling study which is primarily designed to estimate the effect of systemic exposure to LPS or GM-CSF challenge on soluble and cellular inflammatory biomarkers in cantharidin-induced skin blister model. There are no formal hypotheses to be tested.

10.1. Sample Size Determination

Participants will be randomised into the study, in a 1:1 randomisation ratio to either LPS or GM-CSF challenge. It is estimated that up to 16 participants may be evaluated at the optimal dose (8 participants for each challenge agent).

- Part I (up to 28 participants): Up to 6 cohorts of 4 participants (2 for each challenge) may be enrolled. A further 4 participants (2 for each challenge) will be enrolled into the cohort at the optimal dose selected.
- Part II (up to 8 participants): Based on the decisions from an interim analysis following Part I of the study, an additional cohort of up to 8 participants (4 for each challenge) may be enrolled into the cohort at the optimal dose selected.
- For Part I and II (up to 4 participants), if participants prematurely discontinue the study, additional replacement participants may be recruited. A 10% drop-out rate has been assumed.

These numbers have been determined partly through feasibility but considerations has also been given for this study to generate data that can provide the foundation for future

CONFIDENTIAL

studies testing the effect of compounds that target key pathways in inflammatory and autoimmunity. The 2-stage design provides an efficient way to adapt the sample-size, based on emerging data from Part I, so that estimates of response and variability of primary endpoints can be generated.

Following assessment of past studies from literature and GSK, no direct estimates of primary endpoints based on LPS and GM-CSF challenges within a cantharidin-induced skin blister model were reported. However, estimates of inflammatory response for circulating TNF- α and IL-6 which may be translatable to those observed in this study at the optimal dose selected have been reported, albeit with some degree of uncertainty :

- Estimates for circulating urinary tetranor PGDM and total leukocyte numbers are very limited and Part I of the study aims to generate in-house estimates to inform sample size.
- It is assumed for the purposes of sample size calculation, that the between subject standard deviation on the log_e scale for TNF-α and IL-6 are 0.217 and 0.394 respectively (GSK study EMI114416). These estimates reflect the variability of cytokines within a cantharidin-induced skin blister model, albeit in the absence of challenge agent.
- Based on published data (Suffredini, 1999, Dillingh, 2014, Ferguson, 2014, Kiers, 2017) fold increases from baseline were observed in the range of 42 to 200 for TNF- α and 100 to 300 for IL-6 using an IV 1 ng/kg (10EU/ng) LPS challenge. Variability was reported with limited estimates to be directly used for sample size calculations.

Using an estimate of SD the log_e scale = 0.217 (EM114416) for TNF- α and a sample size of 4 and 8 participants, the probability that the true ratio between systemic challenge and baseline being greater than 1 can be calculated for a range of unknown true differences. . 3 below shows the probability of success for the stated assumptions, for a range of true treatment ratios.

[figure not shown]

Figure 3 Probability of Success for Cytokines

For example, the probability of achieving study success (i.e. based on observed fold increases from baseline in literature and therefore representing robust inflammatory cytokine responses with the challenge) assuming the true increase of cytokines with challenge agent over baseline is 40% (ratio of 1.4) is greater than 90% (for n=4 and 8 participants). If the truth is that there is no increase over baseline (ratio=1) then there is a 10% chance of incorrectly declaring success.

Sample Size Sensitivity

Table 1, provides the probability of achieving study success assuming the true increase of cytokines with challenge agent over baseline is 40% (ratio of 1.4) and assuming larger variability is observed.

Assumed SD	True Ratio	Probability of Success (%)		
(Loge scale)	(Challenge/Baseline)	n = 4	n = 8	
0.394 [1]	1.4	66%	87%	
0.434 [2]	1.4	61%	82%	
0.473 [3]	1.4	56%	77%	
[1] Higher variability observed in study EMI114416; [2] Increase of 10% for SD=0.394; [3] Increase of 20% for SD=0.3984				

Table 1 Probability of Success for Cytokines Assuming Higher Variability Observed Observed

Sample Size Re-estimation

Sample size re-estimation will be conducted following Part I of the study. If there is an increase in the precision of estimates for inflammatory responses, then additional participants will be enrolled.

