**Table 1 Changes to Protocol Defined Analysis Plan**

[figure not shown]
Protocol	Reporting & Analysis Plan	
Statistical Considerations	Statistical Analysis Plan	Rationale for Changes

 
Sample size re-estimation will be conducted following Part I of the study.
 
	
 
Sample size re-estimation will not be conducted
 
	
 
The methodology used for the original sample size calculation is no longer applicable, therefore the sample size re-estimation will not be conducted. Instead a set of criteria outlined in Section 3.2 will be used to decide if additional participants will be enrolled in Part II of the study.
 

 
Randomized Population (All participants who are randomized to receive and are given the treatment (LPS or GM-CSF challenge)) is defined as one of the analysis population.
 
	
 
Randomized Population will not be used for Analysis
 
	
 
The randomized and safety populations have the same definitions. Hence only safety population would be used.
 

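### The probability of success above 90% that Protocol 10.1 states for cytokines holds for TNF-α only; at the protocol's own IL-6 SD it is 66% (n=4) and 87% (n=8)

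*Protocol*

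**What the plan says.** Both cytokines are primary endpoints for LPS (Protocol Section 4; SAP Section 2.2). For the sample size calculation, Protocol Section 10.1 assumes that the between-subject "standard deviation on the log_e scale for TNF-α and IL-6 are 0.217 and 0.394 respectively". It adds that these SDs come from the blister model, "albeit in the absence of challenge agent".

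The calculation then takes one of the two values: "Using an estimate of SD the log_e scale = 0.217 (EM114416", for TNF-α, with "a sample size of 4 and 8 participants". Figure 3 is titled for cytokines in general. The worked example says that, for a true challenge/baseline ratio of 1.4 in cytokines, the probability of success "is greater than 90% (for n=4 and 8 participants", with a 10% chance of false success at a ratio of 1.

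Table 1, under a sensitivity sub-heading, gives 66% (n=4) and 87% (n=8) for SD 0.394. Its footnote describes that SD only as "Higher variability observed in study EMI114416". The other two rows raise 0.394 by 10% and 20%.

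The SAP (Section 2.1, Table 1) drops the sample size re-estimation because "The methodology used for the original sample size calculation is no longer applicable".

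**The concern.** The SD of 0.394 is introduced as the planning value for IL-6. A few lines later it reappears, without the name IL-6, as a pessimistic scenario. A reader of the worked example would conclude that four participants per agent give better than 90% probability of success for either cytokine. For IL-6 the protocol's own assumptions say otherwise at both sample sizes. The real IL-6 sensitivity rows are the 0.434 and 0.473 rows, at 61%/82% and 56%/77%.

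What is at stake is an accurate account of what 4 and 8 participants deliver for each primary cytokine. The study is meant to supply estimates on which later studies are planned, and the SAP offers no replacement for these figures.

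**Working it through.** **Inputs (Protocol 10.1).** SD on the log_e scale: 0.217 (TNF-α), 0.394 (IL-6). n = 4 and 8. True ratio 1.4, so ln 1.4 = 0.3365. False-success rate 10%. Success means a ratio above 1, which I read as one-sided: z = 1.2816.

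**Step 1: reproduce the protocol.** One-sample formula on the log ratio, SD treated as known:

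P = Φ(ln 1.4 × √n / SD − 1.2816)

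- TNF-α, n=4: Φ(0.3365 × 2 / 0.217 − 1.2816) = Φ(1.82) = 96.6%
- IL-6, n=4: Φ(0.3365 × 2 / 0.394 − 1.2816) = Φ(0.43) = 66.5%
- IL-6, n=8: Φ(0.3365 × 2.828 / 0.394 − 1.2816) = Φ(1.13) = 87.2%

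| SD | n=4 stated | n=4 computed | n=8 stated | n=8 computed |
|---|---|---|---|---|
| 0.217 (TNF-α) | >90% | 96.6% | >90% | 99.9% |
| 0.394 (IL-6) | 66% | 66.5% | 87% | 87.2% |
| 0.434 | 61% | 60.6% | 82% | 81.9% |
| 0.473 | 56% | 55.6% | 77% | 76.7% |

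Every stated figure is reproduced to within one percentage point. Other readings do not fit the 0.394 row: two-sided 10% gives 53%/78%, a two-sample comparison 47%/67%, and a one-sample t test 57%/84%. So the protocol's method is one-sided 10% with the SD treated as known.

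**Step 2: when does the figure exceed 90%?** Solving for the SD at P = 90%: SD ≤ 0.3365 × √n / (2 × 1.2816), which is 0.263 at n=4 and 0.371 at n=8. The IL-6 SD of 0.394 is above both limits. At that SD, 90% needs a true ratio of about 1.66 (n=4) or 1.43 (n=8).

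**Step 3: SD estimated rather than known.** Replacing the normal by the noncentral t on n−1 degrees of freedom, with the one-sided 10% t cut-off:

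| Endpoint | n=4 | n=8 |
|---|---|---|
| TNF-α | 90.9% | 99.8% |
| IL-6 | 57.2% | 83.8% |

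If the cut-off stays at 1.2816 while the SD is estimated, false success is P(t on 3 df > 1.2816) = 14.5% at n=4 and P(t on 7 df > 1.2816) = 12.0% at n=8, against the stated 10%.

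**Step 4: which SD?** The quantity is a within-participant log ratio, but the SD entered is between-subject. With equal variances before and after challenge, the SD of the log ratio is SD × √(2(1−ρ)), which equals the SD only at ρ = 0.5. The SAP (Sections 5.2 and 7.1.2) takes the baseline for circulating TNF-α and IL-6 from Session 2 Day 1, so ρ is a within-session correlation. The documents give no value for it. Assuming ρ from 0 to 0.75, with the SD known:

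| Endpoint | n=4 | n=8 |
|---|---|---|
| TNF-α | 82% to 99.9% | 96.6% to about 100% |
| IL-6 | 47% to 87% | 67% to 98% |

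**Step 5: illustrative precision.** The 95% interval for the ratio is the estimate multiplied or divided by exp(t × SD / √n), with t = 3.182 (n=4) or 2.365 (n=8), at ρ = 0.5:

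- IL-6: exp(3.182 × 0.394 / 2) = 1.87 at n=4; 1.39 at n=8
- TNF-α: 1.41 at n=4; 1.20 at n=8

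**The case against.** The calculation announces that it uses the TNF-α SD, no sentence gives more than 90% for SD 0.394, and Table 1 prints the lower values in the same section. That stands: nothing is miscalculated, and a careful reader can recover the IL-6 result. It does not rescue the general wording of the worked example and the Figure 3 title, or the missing IL-6 label in Table 1.

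The consequence is also limited. Sections 10 (Protocol) and 2.4 (SAP) state that there are no formal hypotheses. The ratio of 1.4 is only an example, while Section 10.1 cites increases of 42- to 200-fold for TNF-α and 100- to 300-fold for IL-6. Those come from 1 ng/kg at 10 EU/ng (10 EU/kg), against 0.75 × 6 = 4.5 EU/kg at the dose reported in SAP Section 3.1, so they may not carry over exactly. The margin is still very wide: at SD 0.394 and a ratio of only 2, the t-based probability at n=4 is already 95%. Escalation and Part II entry (SAP Sections 3.1 and 3.2) use other thresholds.

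The estimated-SD figures are a substitute for the planned analysis. Protocol Section 10.3 plans a Bayesian repeated-measures model and states no prior, so the t result corresponds only to a vague prior. The 66% and 87% need no such assumption.

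**Conclusion.** As worded for cytokines, the claim of more than 90% is wrong for IL-6 at both sample sizes: 66% and 87% on the protocol's own SD and method. It is right for TNF-α (about 97% and 99.9%), given a known SD and ρ = 0.5. Estimating the SD costs IL-6 about 9 points at n=4 and 3 at n=8. It leaves TNF-α just above 90% at n=4, and a low correlation would take TNF-α below 90% there. All of this rests on SDs from unchallenged blisters, not from circulating cytokines after LPS.

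Three stronger readings are tempting, and the documents do not support them:

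- A reader might infer that TNF-α and IL-6 must both succeed. The protocol lists both as primary but never calls them co-primary or requires joint success.
- A reader might infer that these probabilities are the sole basis for 4 and 8 per agent. Section 10.1 also cites feasibility and the aim of generating in-house estimates, and it says that estimates for urinary tetranor PGDM and leukocytes are very limited.
- A reader might infer that dose or Part II decisions are compromised. They do not use this success rule.

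This is a fault of labelling and generalisation, worth correcting, with small practical weight.

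**What to change.** In Protocol Section 10.1:

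- State the result per endpoint with the SD treated as known: TNF-α about 97% (n=4) and 99.9% (n=8); IL-6 66% and 87%.
- Name TNF-α in the worked example and in the Figure 3 title.
- In Table 1, label the 0.394 row as the IL-6 base case, and 0.434 and 0.473 as the IL-6 sensitivity rows. Footnote [3] prints 0.3984 where 0.394 is meant (0.394 × 1.2 = 0.473).
- State that the SD is treated as known, and that a between-subject SD stands in for the SD of the within-participant log ratio, which is exact only with equal variances and a baseline/post-challenge correlation of 0.5.
- Add as a caveat the estimated-SD figures (TNF-α about 91%/99.8%; IL-6 57%/84%), and note that the 10% false-success rate holds only if the cut-off allows for estimating the SD.
- If precision is given, mark the interval factors (IL-6 1.87 and 1.39; TNF-α 1.41 and 1.20) as illustrative, because the SDs come from blisters without challenge.

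If the protocol will not be amended again, a short note in the SAP version for final reporting would do. The cost is wording and a less favourable IL-6 figure; the design and the number of participants do not change.
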